## 1.0 Objectives / Specific Aims

**Study Aim: Quantify the phenotypic-related brain states of MDD patients compared to healthy individuals using a novel INSCAPE neuroimaging method and identify dynamic biomarkers that can track brain recovery of MDD patients over an antidepressant course of TMS therapy.**

In this study, we plan to apply our novel “Individualized Network-based Single-frame Coactivation Pattern Estimation” (INSCAPE) method in 20 patients with Major Depressive Disorders (MDD) and 20 healthy controls to identify MDD-related brain states. We will then track changes in MDD-related brain states while MDD patients are undergoing 6 weeks of transcranial magnetic stimulation (TMS) therapy. Three separate neuroimaging visits will be conducted at the MUSC [name] imaging center before, during, and after 30 sessions of the standard-of-care TMS treatment from the MUSC Brain Stimulation Service (~6 weeks in total). Additionally, healthy participants will undergo 3 times of MRI scanning with a 3-week interval between each two MRI sessions.

*Hypothesis: INSCAPE method can identify MDD specific brain states and track brain circuits recovery during TMS therapy.* We intend to establish INSCAPE as an effective neuroimaging technique to track antidepressant response in MDD patients undergoing 6 weeks of TMS therapy. We hypothesize that a) our INSCAPE method will be able to quantify phenotypic differences between MDD patients before TMS therapy and compared to healthy individuals. We further hypothesize that we can b) track the renormalization of brain state during the course of TMS treatment, as patients transition from “depressed brain states” to more “healthy” brain states. Lastly, we c) identify whether baseline brain state dynamic measures can predict response to TMS based on behavioral measures of response to TMS treatment.

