An advancement in rs-fMRI is a novel dynamic analytic approach which examines absolute coactivation patterns of BOLD signal across the brain at each time point (14). Using this method, we have already found brain states of psychiatric phenotypes in schizophrenia and psychotic experience patients, which can track with psychotic symptom severity (15). Based on this, our group has further developed a new method of detecting robust, dynamic brain states at the individual level, called INSCAPE – Individualized Network-based Single-frame Coactivation Pattern Estimation. INSCAPE can detect phenotypic differences amongst different individuals based on brain state (16). Our

findings indicated that the occurrence rate of brain states related to brain laterality could predict language lateralization derived from a semantic decision task and distinguish genders and handedness. Additionally, we also found a brain state that can track longitudinal brain recovery from stroke over six months – the occurrence rate of this brain state continuously reduced to the normal level during inter-hemispheric communication restoration. Thus, INSCAPE is a novel and advanced method that can allow us to begin understanding functional brain state changes that occur over the course of antidepressant treatment track recovery.

Ultimately, this study begins to optimize antidepressant treatments by identifying individual differences in brain states amongst patients. These individual differences likely play a large role in response rate, as well as network restoration in MDD patients. Thus, if successful, neuroimaging can become an additional tool that can be used before undergoing TMS treatment to better predict and improve treatment outcomes.

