### 4.0 Study Endpoints (if applicable)

**Primary Outcome:** *Dynamic brain states changes relative to MDD.*

The main outcomes of this study are neuroimaging related dynamic parameters derived from our INSCAPE approach, including occurrence rate, dwell time, transition matrix, etc. These outcomes will be compared between depression patients and healthy individuals. Moreover, we will also estimate the renormalization of brain states by quantifying the continuous changes of functional imaging measures as patients improve over the course of TMS treatment, moving towards the level of healthy controls. Lastly, the psychiatric-related imaging measures at baseline will then be verified whether they can predict symptom improvement and response to TMS therapy.

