## 10.0 Study Design / Methods

1. *Study Overview:* After determining eligibility and interest, written informed consent will be obtained from participants at the MUSC Center for Biomedical Imaging. Enrolled MDD patients (n=20) will be involved in neuroimaging before, during, and after 30 sessions of the standard-of-care TMS treatment MUSC brain stimulation service (~6 weeks in total). For each neuroimaging visit, participants will be placed in the MRI scanner and undergo four runs of resting-state fMRI (6 min/run). During the scanning, participants will be

asked to stay still in the scanner. Additionally, enrolled healthy control participants (n=20) will undergo 3 sessions of MRI scanning over a 6-week interval (Baseline, week 3, week 6). Upon completion of the 30 minutes neuroimaging visit, participants will be compensated \$50. A timeline and group assignment overview are demonstrated in **Figure 1**.

**Figure 1.** Study Overview.

2. *Recruitment, Screening, and Consent Procedures:* MDD patients will be recruited from the Brain Stimulation Service at MUSC by the clinical care team. Patients who are found to be appropriate candidates for TMS for MDD will be offered to be screened for enrollment into the study protocol.

Healthy participants will be recruited from the MUSC community (students and staff) as well as general population from the greater Charleston region. We will recruit via flyers around campus and word of mouth. If interested in learning more about the study, potential subjects will be phone screened and educated regarding the study's details. If interested in participating in the study, they will be consented and enrolled into the study's protocol. After consent, the participant will complete a demographics and intake form.

3. *Pregnancy Test Procedures:* If participants are individuals of childbearing potential, they will be provided with a pregnancy test strip. After completing the pregnancy test, participants with negative results will be asked to continue to the remaining study procedures, whereas those with a positive result will be debriefed and released.

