4. *Neuroimaging Procedures:* All MRI imaging will be performed using a Siemens 3.0 T Prisma scanner equipped with a 32-channel head coil. All MRI scan visits will be held at the MUSC Center for Biomedical Imaging (CBI; see the Facilities and Resources section). Each MRI scan session will include a high-resolution T1-weighted structural scan (whole brain sagittal acquisition, 224 slices, TR=2530ms, TE=3.65ms, TI=1100ms, 1mm thick slices, FOV=256, 256x176, flip angle = 7 degrees.), followed by four runs of resting-state fMRI scans using a gradient-echo echo-planar pulse sequence (TR = 2000 ms, TE = 36 ms, FA = 80°, 2.2 × 2.2 × 2.2-mm voxels).
5. *Depression/Anxiety Assessments:* MDD participants will complete several standardized assessments performed prior to starting TMS treatment, and repeated on weekly intervals. The assessments to be performed are the Beck Depression Inventory II (BDI-II), Hamilton Anxiety Rating Scale (HAM-A), Hamilton Depression Rating Scale (HAM-D), and Patient Health Questionnaire 9 (PHQ-9). These assessments will be used to describe more accurately clinical changes in depression over the course of TMS, and will be used alongside the collected MRI data to potentially identify changes to the brain associated with clinical improvement or lack thereof.

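### If the MDD-related states, or the direction that counts as recovery, are read from the same participants' baseline gap, part of the closure by week 3 is regression to the mean

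*Protocol*

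**What the plan says.** Section 1.0 (Objectives / Specific Aims) applies INSCAPE in 20 patients and "20 healthy controls to identify MDD-related brain states". The next sentence is "We will then track changes in MDD-related brain states while MDD patients are undergoing 6 weeks of transcranial magnetic stimulation (TMS) therapy". Hypothesis (a) is that the method can "quantify phenotypic differences between MDD patients before TMS therapy and compared to healthy individuals", which is the baseline contrast. Hypothesis (b) is that brain states renormalize during TMS.

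Section 4.0 (Study Endpoints) describes renormalization as "quantifying the continuous changes of functional imaging measures as patients improve over the course of TMS treatment, moving towards the level of healthy controls". Its list of measures is open-ended, and no state or direction is named in advance. Section 6.0 enrols 40 people in total, and no separate sample for choosing states is described. Under Section 10.0, controls are scanned at baseline, week 3 and week 6.

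**The concern.** A state that enters the tracked set because patients and controls differ on it at baseline has, on average, an observed gap larger than its true gap. The excess is visit noise that will not recur. At the first rescan the gap shrinks even if nobody has changed, and it shrinks in the direction that hypothesis (b) predicts. The same happens with no filter at all if toward controls is defined by the sign of the observed baseline gap.

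The controls' rescans look like a safeguard but do not work as one here. Noise in both groups produced the inflated gap, so controls regress in the opposite direction by the same amount. A group-by-visit comparison carries both halves, and the patients' own change carries one.

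At stake is the main longitudinal claim. The Background (Section 2.0) offers the same kind of evidence as its precedent for recovery, from stroke: "the occurrence rate of this brain state continuously reduced to the normal level during inter-hemispheric communication restoration".

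**Working it through.** There is no stated figure to reproduce: the protocol gives no significance level, effect size, SD or test-retest reliability.

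**Inputs from the protocol.** 20 per group; scans at baseline, week 3 and week 6.

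**Assumed inputs.** Each measure is a stable person value (variance ICC) plus visit noise (variance 1 − ICC), total SD 1. ICC is 0.3, 0.5, 0.7 or 0.9. The true gap δ is 0, 0.5 or 0.8 SD. There is no true change in either group. A measure is kept if the baseline two-sample t-test gives p<0.05.

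**Why the selected gap is inflated.** With 38 degrees of freedom the critical t is 2.024, so the observed gap must exceed about 2.024 × √(2/20) = 0.64 SD. A measure with a true gap of 0.5 SD passes only when noise helps it; in simulation it passes about 34% of the time. The mean selected baseline gap g is 0.72 SD at δ = 0, 0.833 at δ = 0.5 and 0.956 at δ = 0.8.

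**Expected rescan gap with no change:** δ + ICC × (g − δ).
**Share of the gap lost:** (1 − ICC) × (g − δ)/g.

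- δ = 0: (g − δ)/g = 1.
- δ = 0.5: 0.333/0.833 = 0.40.
- δ = 0.8: 0.156/0.956 = 0.163.

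| True gap | ICC 0.3 | 0.5 | 0.7 | 0.9 |
|---|---|---|---|---|
| 0 (null) | 70% | 50% | 30% | 10% |
| 0.5 SD | 28% | 20% | 12% | 4% |
| 0.8 SD | 11% | 8% | 5% | 2% |

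Simulation agrees; the 0.8 SD, ICC 0.3 cell came out at 11% or 12% in different runs. At δ = 0.5 and ICC 0.5 the formula gives 0.5 + 0.5 × 0.333 = 0.667, and the simulated gaps are 0.670 at week 3 and 0.667 at week 6. Patients moved −0.083 SD and controls +0.082 SD. The drop is therefore complete by week 3 and split equally between the groups.

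**False convergence, baseline to week 6, group-by-visit** (nominal 2.5% in that direction, ICC in the same order):

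- selected nulls: about 23, 18, 12 and 7% (up to 24% across runs);
- true 0.5 SD: 6.4, 5.8, 5.2 and 4.1%;
- true 0.8 SD: 3.5, 3.4, 3.3 and 3.0%.

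The patients' own paired test errs in about 14, 10, 8 and 5% for selected nulls, and in roughly 3 to 6% for true states.

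**Week 3 to week 6.** False convergence was 2.2 to 3.0% in every setting, so this interval carries no such bias when selection and direction use baseline only.

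**Every measure kept, direction read from the observed baseline gap.** Null measures still lose 70, 50, 30 and 10% of the gap. Their significant group-by-visit changes run 3.4 to 4.8% toward controls and 0.3 to 1.5% away. At a true 0.5 SD, 10, 7, 4 and 1% of the gap is lost.

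**Selection and direction both taken from other participants.** The mean change was within 0.01 SD of zero in all 12 settings.

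**The case against.** The strongest reply is that the protocol writes no selection rule, and that a SAP, not shown here, could supply one. Section 4.0 lists measures to be compared and then tracked, without restricting tracking to those that differ at baseline. The phrase "the psychiatric-related imaging measures at baseline will then be verified whether they can predict symptom improvement and response to TMS therapy" belongs to the prediction aim, so it does not define what is tracked under (b). In Section 1.0 the word *then* fixes an order and not a significance filter.

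This stands in part. A reader might infer that the protocol prescribes selection by a baseline test. It does not; that is the natural reading of identify-then-track, and the point must stay conditional. It is still more than absent detail, because the protocol itself fixes the sequence and the meaning of renormalization, and a SAP that follows them can inherit the bias.

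A reader might also infer that most of any renormalization found would be artefact. The figures do not support that. The large ones apply to null measures that pass an assumed uncorrected filter. With 8 independent measures and no true difference anywhere, about 66% of trials would select nothing.

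A third tempting inference is that following every measure settles the matter. It does not if direction still comes from the observed gap.

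The design does offer partial help: the week 3 to week 6 interval, and weekly symptom scales that "will be used alongside the collected MRI data to potentially identify changes to the brain associated with clinical improvement or lack thereof". Neither corrects the change from baseline to week 3.

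**Conclusion.** The concern holds in conditional form and should be fixed; confidence is medium. If states or direction are taken from the observed baseline gap in the same people, the change from baseline to the first rescan is biased toward hypothesis (b), and the control scans do not cancel it. Under the assumptions above, the bias takes from about 12% down to 2% of the selected gap at a true 0.8 SD, 28% down to 4% at 0.5 SD, and 70% down to 10% for nulls, as ICC rises from 0.3 to 0.9. False group-by-visit convergence is about 3 to 6% for truly different states and 7 to 24% for selected nulls, against 2.5%. For large differences in reliable measures the effect is modest. The documents do not show that hypothesis (b) cannot be tested, or that the sponsor intends a baseline filter.

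**What to change.** Add one sentence to each of Sections 1.0 and 4.0, for example: *For estimating renormalization, both the MDD-related states and the direction of abnormality will be set without the baseline scans of the participants in whom change is measured, by cross-fitting (select and sign in the other participants, estimate change in the held-out participants) or from earlier independent data.*

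Also report baseline to week 3 and week 3 to week 6 separately. State that only the second interval is free of this bias when selection and direction use baseline only, and that it misses early change.

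The cost is more computing and a less precise, probably smaller, estimate of renormalization. No new scans or participants are needed.

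Following all measures with family-wise control (permutation max-T) is an optional alternative and not a requirement. It tests for any differential change, not for movement toward controls. Against select-then-test, with 8 measures of which 2 truly differ and a gap that closes fully by week 6, its power per truly different state at ICC 0.3, 0.5, 0.7 and 0.9 is 24, 38, 65 and 100% against 47, 55, 65 and 70% at 0.8 SD. At 0.5 SD it is 7, 10, 21 and 74% against 16, 19, 24 and 31%. Power is thus lost at low reliability and gained at high reliability.

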## 2.0 Background

Major depressive disorder (MDD) is a prevalent psychiatric disorder characterized by impairments in affect, behavior, and cognition. Individuals with MDD persistently suffer from feelings of sadness and worthlessness and experience less enjoyment in social interactions (1-3). Over 21 million adults have had at least one major depressive episode, which leads to job absenteeism and reduces productivity, and has been one of the highest causes of disability worldwide that creates a tremendous economic burden in society (3-5). Aside from conventional antidepressant medications, transcranial magnetic stimulation (TMS) has emerged as an effective second-line intervention for medication-resistant depression (6, 7). Although TMS delivered to the left dorsolateral prefrontal cortex (dlPFC) is used clinically for the treatment of depression, it remains limited by large heterogeneity in clinical response between patients (8). One factor contributing to this wide range of individual response rates is a limited understanding of the changes induced in neural circuits that drive TMS response. Thus, investigating the functional circuits underlying depression at the individual level can help lead to more effective treatments for depression.

Resting-state functional magnetic resonance imaging (rs-fMRI) is a promising technique for assessing functional connectivity (FC) between brain regions that exhibit spontaneous synchronous fluctuations (9). Our previous rs-fMRI studies have revealed depressive-related functional connectivity (FC) changes in the default mode network (DMN) track with the severity of depression symptoms, including the anterior cingulate cortex, angular gyrus, and inferior parietal lobe (3, 10). Additionally, recent rs-fMRI advances have enabled the delineation of the spatial configuration of networks at the individual level (11). This individual-level analysis, rather than group-based averaging, has led to the discovery of new subnetworks in individuals that were missed in the group-average maps (12) and achieved higher accuracy in predicting phenotypes and disease symptoms based on functional measures (13). Therefore, exploring subnetworks of DMN at the individual level may help discover new biomarkers for depression treatment.

An advancement in rs-fMRI is a novel dynamic analytic approach which examines absolute coactivation patterns of BOLD signal across the brain at each time point (14). Using this method, we have already found brain states of psychiatric phenotypes in schizophrenia and psychotic experience patients, which can track with psychotic symptom severity (15). Based on this, our group has further developed a new method of detecting robust, dynamic brain states at the individual level, called INSCAPE – Individualized Network-based Single-frame Coactivation Pattern Estimation. INSCAPE can detect phenotypic differences amongst different individuals based on brain state (16). Our

findings indicated that the occurrence rate of brain states related to brain laterality could predict language lateralization derived from a semantic decision task and distinguish genders and handedness. Additionally, we also found a brain state that can track longitudinal brain recovery from stroke over six months – the occurrence rate of this brain state continuously reduced to the normal level during inter-hemispheric communication restoration. Thus, INSCAPE is a novel and advanced method that can allow us to begin understanding functional brain state changes that occur over the course of antidepressant treatment track recovery.

Ultimately, this study begins to optimize antidepressant treatments by identifying individual differences in brain states amongst patients. These individual differences likely play a large role in response rate, as well as network restoration in MDD patients. Thus, if successful, neuroimaging can become an additional tool that can be used before undergoing TMS treatment to better predict and improve treatment outcomes.

### 3.0 Intervention to be studied (if applicable)

This study is a neuroimaging study, thus, there is no intervention need to be managed for this study. Although, participants will be patients receiving the standard-of-care TMS therapy as part of their normal treatment plan in the MUSC Brain Stimulation Service, this intervention is not part of the study procedures.

### 4.0 Study Endpoints (if applicable)

**Primary Outcome:** *Dynamic brain states changes relative to MDD.*

The main outcomes of this study are neuroimaging related dynamic parameters derived from our INSCAPE approach, including occurrence rate, dwell time, transition matrix, etc. These outcomes will be compared between depression patients and healthy individuals. Moreover, we will also estimate the renormalization of brain states by quantifying the continuous changes of functional imaging measures as patients improve over the course of TMS treatment, moving towards the level of healthy controls. Lastly, the psychiatric-related imaging measures at baseline will then be verified whether they can predict symptom improvement and response to TMS therapy.

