## 6.0 Number of Subjects

We will enroll 40 total participants into this study (n=20 patients with depression and n=20 healthy adults) for this study.

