## 7.0 Setting

Volunteers with Major Depressive Disorder who are candidates for TMS will be consented and educated about the study in a private screening area at either the MUSC Brain Stimulation Service or the MUSC [name] Center for Biomedical Imaging, whatever is most convenient for the participant. Healthy volunteers will be consented at MUSC [name] Center for Biomedical Imaging.

All neuroimaging conducted in this study, for both healthy volunteers and depressed volunteers, will be completed at the MUSC [name] Center for Biomedical Imaging.

Depressed volunteers will complete the additional standardized mood assessments at the MUSC Brain Stimulation Service during their scheduled standard-of-care TMS treatment visits at the MUSC Brain Stimulation Service. Depressed volunteers will receive standard-of-care TMS treatment at the MUSC Brain Stimulation Service.

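### Should the healthy week-3 scans have been spent on more TMS patients, to sharpen the prediction of treatment response?

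*Protocol*

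**What the plan says.** Protocol section 6.0 sets the size: "We will enroll 40 total participants into this study (n=20 patients with depression and n=20 healthy adults) for this study". Section 10.0, item 1, fixes the scan schedule in both groups. For patients: "Enrolled MDD patients (n=20) will be involved in neuroimaging before, during, and after 30 sessions of the standard-of-care TMS treatment". For controls: "enrolled healthy control participants (n=20) will undergo 3 sessions of MRI scanning over a 6-week interval (Baseline, week 3, week 6".

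The outcome side of the prediction question comes from clinical scales. Section 10.0, item 5, states that "MDD participants will complete several standardized assessments performed prior to starting TMS treatment, and repeated on weekly intervals", and section 7.0 places them in clinic visits that take place anyway: "Depressed volunteers will complete the additional standardized mood assessments at the MUSC Brain Stimulation Service during their scheduled standard-of-care TMS treatment visits".

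Prediction appears twice. Section 1.0 gives it as the third hypothesis: "identify whether baseline brain state dynamic measures can predict response to TMS based on behavioral measures of response to TMS treatment". Section 4.0 gives it as the closing sentence under the only endpoint heading, Primary Outcome: "the psychiatric-related imaging measures at baseline will then be verified whether they can predict symptom improvement and response to TMS therapy". The Study Aim that opens section 1.0 names two goals, comparing brain states between patients and healthy people and tracking recovery over the TMS course. Prediction is not in it. The protocol gives no power, precision, effect size or variance for any of the three questions.

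**The concern.** Prediction stands under the Primary Outcome heading, and nothing there marks it as secondary. It needs one baseline scan per treated patient plus the weekly scales, so it draws on 20 scans of 120. Another 20 scans go to healthy people at week 3. These cannot be paired with a TMS outcome, are not needed for the baseline group comparison, and would have zero weight in a straight-line healthy trend over weeks 0, 3 and 6.

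The scanner time therefore looks misallocated. With 20 patients, a moderate observed correlation cannot be told apart from none, and estimates that happen to reach significance are on average too large. A statistical analysis plan cannot repair this, because it can neither add patients nor move scans. If the healthy week-3 scans really had no use, the trial would be giving up a 32% narrower interval for nothing.

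**Working it through.** **Inputs from the protocol.** 20 patients and 20 controls, three scans each (sections 6.0 and 10.0). Prediction uses the patients' baseline scans and weekly scales (sections 4.0 and 10.0). The protocol states no precision figure for prediction, so there is none to reproduce.

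**Scan counts.**
- Planned: 20×3 + 20×3 = 120.
- Exchange (controls at baseline and week 6 only, 20 extra patients scanned once): 20×3 + 20×2 + 20×1 = 120.
- Addition (all healthy scans kept, 27 extra baseline-only patients): 120 + 27 = 147.

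**Precision of a correlation.** The 95% half-width on the Fisher z scale is 1.96/√(n−3).
- n = 20: 1.96/√17 = 0.475.
- n = 40: 1.96/√37 = 0.322. Ratio √(17/37) = 0.678, so 32% narrower.
- n = 47: ratio √(17/44) = 0.622, so 38% narrower.
- Observed r = 0.4: −0.05 to 0.72 with 20 patients, 0.10 to 0.63 with 40.
- Observed r = 0.3 with 40 patients: −0.01 to 0.56, which still reaches from no association to a strong one.

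The 32% depends on n alone. It would be the same for any correlation in any study of 20 people, so it does not show a fault particular to this protocol.

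**What the exchange costs in patients.** Patients rise from 20 to 40 and total enrolment from 40 to 60. With four scales at baseline and in each of about six weeks, the extra ratings number 4 × 7 × 20 = 560. If only 5, 10 or 15 extra patients are found, the narrowing is 1 − √(17/22) = 12%, 1 − √(17/27) = 21% or 1 − √(17/32) = 27%. The protocol does not give recruitment capacity, and nothing in it shows that scanner time is the tighter limit.

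**What the exchange costs in information.** Write P and C for the patient and control means, with subscripts for the week, taking the mid-treatment patient scan as week 3.
- The control-adjusted change at mid-treatment is (P3 − P0) − (C3 − C0).
- Without C3, the control change has to be interpolated as (C6 − C0)/2.
- The resulting bias is (C3 − C0) − (C6 − C0)/2. It is zero only if the healthy course is linear, and data without C3 cannot test that.
- The slope weights at weeks 0, 3 and 6 are −1/6, 0 and 1/6, so the week-3 scan has zero weight only in a fitted straight line. With visit treated as a category, it is the sole control for the mid-treatment scan.

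Section 4.0 compares patients with healthy individuals without limiting this to baseline, and follows patients' change over the course of treatment against the healthy level. It specifies no linear model.

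**Cost to another contrast.** For patients' week-6 mean minus the pooled healthy level, the SE ratio is √[(1/20 + (1+ICC)/40) / (1/20 + (1+2·ICC)/60)]. This gives 1.037, 1.025 and 1.014 at ICC 0.3, 0.5 and 0.7 (assumed values, since the protocol gives none). These small losses do not cover the week-3 contrast, which disappears altogether.

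**Inflation of significant estimates.** With 20 patients the two-sided 5% critical value is |r| = 0.444. At a true r of 0.5, a significant estimate between 0.444 and 0.5 lies below the truth. So it is wrong that every significant estimate is inflated. The average is: simulated mean inflation is 19% at true r = 0.5 and 42% at true r = 0.4.

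**The case for a change.** The strongest case for the concern is that section 4.0 does list prediction under its only outcome heading and speaks of verifying it, that only 20 scans can be paired with a TMS outcome, and that the protocol gives no separate reason for the healthy week-3 scan. The exchange would also help the baseline patient-control comparison: at 40 against 20 its SE falls by 1 − √[(1/40 + 1/20)/(1/20 + 1/20)] = 13%. A sponsor unwilling to lose healthy scans could add 27 baseline-only patients instead. At the least, prediction could be labelled exploratory at no cost.

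The counts and gains stand. The inference does not.

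- The healthy schedule mirrors the patient schedule, which is the ordinary reason for a longitudinal control group and needs no separate justification scan by scan. It serves one of the two goals in the Study Aim, whereas prediction is absent from that aim and comes last in both sections that mention it.
- Healthy scans are not wholly idle for prediction either. The predictors are the psychiatric-related measures, which plausibly come from the patient-control comparison.
- Adding 27 patients is a request for a larger study. The protocol misses no target of its own that would call for one.
- An exploratory label would be sensible wording, but it changes no scan, analysis or result. Ranking prediction as exploratory would also weaken the case for taking scans from the recovery question to serve it.

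**Conclusion.** The concern does not hold. The protocol fixes 20 patients and 20 controls with three scans each and claims no precision for prediction, so there is no stated figure that it fails to meet. The 32% gain is correct as arithmetic, but it is the general effect of doubling n. It requires 20 more TMS patients and gives up the concurrent mid-treatment control. Whether that exchange is worthwhile depends on recruitment capacity, on the shape of the healthy time course and on the weight given to prediction against tracking recovery. The protocol settles none of these in favour of the exchange, and experienced statisticians could choose either design.

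What remains is a caution for reading the results. With 20 evaluable patients the 95% half-width is 0.475 on the Fisher z scale, and an observed correlation of 0.4 is compatible with none. The interval figures assume a single correlation with bivariate normal data and no dropout. With 80% evaluable (16 against 32 patients, an assumption), the gain from doubling would be 1 − √(13/29) = 33%, and the conclusion is the same.

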#### Healthy Individuals:

Additionally, 20 demographic-matched healthy individuals will also be recruited as a control group.

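### Does Section 4.0 restrict the predictors of TMS response to measures that differ from controls, contradict Section 1.0, and so cost the prediction aim its power?

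*Protocol*

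**What the plan says.** Section 1.0, hypothesis (c), is to "identify whether baseline brain state dynamic measures can predict response to TMS based on behavioral measures of response to TMS treatment". That sentence does not limit which baseline measures are used.

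Section 4.0, under the primary outcome, gives an open list of INSCAPE parameters, "including occurrence rate, dwell time, transition matrix, etc. These outcomes will be compared between depression patients and healthy individuals". It goes on to renormalization over the TMS course and ends with prediction: "the psychiatric-related imaging measures at baseline will then be verified whether they can predict symptom improvement and response to TMS therapy". The protocol does not define the term psychiatric-related.

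Elsewhere Section 1.0 speaks of studying patients and "20 healthy controls to identify MDD-related brain states. We will then track changes in MDD-related brain states". There, identification comes before tracking.

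Section 6.0 fixes the size: "We will enroll 40 total participants into this study (n=20 patients with depression and n=20 healthy adults) for this study". The protocol gives no alpha, effect size, power or number of brain states.

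**The concern.** The two sections describe the predictors for the same aim in different words. The sequence in Section 4.0 (compare with controls, then check prediction) and the parallel wording on tracking in Section 1.0 suggest that only measures separating patients from controls go forward.

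Such a screen would be an odd way to choose predictors. Whether a measure differs on average between patients and controls is a between-group property. Whether it predicts improvement is a property of the variation among patients. A true predictor with a small group difference would usually never be tested, and could then be reported as if it did not predict. Under the wider wording of Section 1.0, an open list of measures would be tested and chance findings would be likely. If the choice between the two readings were made after the results were seen, it could change the answer for part of the primary outcome.

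**Working it through.** The protocol has no power figure to reproduce, so the size of the effect has to be built on assumptions.

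**Inputs from the Protocol.** 20 patients and 20 controls (Section 6.0). Measures named: occurrence rate, dwell time, transition matrix, with the list left open (Section 4.0).

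**Assumed.** Normal data; two-sided 5% at each step; all 20 patients evaluable; one outcome scale; true correlation r = 0.6 between the baseline measure and improvement; patient-control difference d = 0.2 to 1.2 SD.

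**Step 1: chance of passing a screen.** Two-sample t-test, 38 df, noncentrality d × √(20/2). For d = 0.5 this is 0.5 × 3.162 = 1.58.

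| d | 0.2 | 0.5 | 0.8 | 1.0 | 1.2 |
|---|---|---|---|---|---|
| Passes | 9.5% | 34% | 69% | 87% | 96% |

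**Step 2: one measure, unadjusted.** The Pearson test in 20 patients at r = 0.6 has 83.5% power by simulation. The Fisher approximation agrees: atanh(0.6) × √17 = 0.693 × 4.123 = 2.86, and Φ(2.86 − 1.96) = 81.5%. Requiring the screen and the Pearson test both to be significant, in the same patients:

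| d | 0.2 | 0.5 | 0.8 | 1.0 | 1.2 |
|---|---|---|---|---|---|
| Both significant | 8% | 28% | 57% | 72% | 80% |

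The apparent loss is therefore real under these assumptions, but it shrinks to about 4 points at d = 1.2.

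**Step 3: the same comparison with equal error control.** Section 1.0 does not offer one pre-chosen measure. K states give K occurrence rates, K dwell times and K(K − 1) transitions, that is K² + K measures: 12, 20 or 72 for an assumed K = 3, 4 or 8. Direct testing applies Bonferroni over all of them. Screened testing applies Bonferroni only over the measures that pass. The table assumes one true predictor with r = 0.6 and independent other measures that neither differ from controls nor predict (simulation, 1,000,000 runs per value of d).

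| Measures | Direct | Screened, d = 0.2 | d = 0.5 | d = 0.8 | d = 1.0 |
|---|---|---|---|---|---|
| 12 | 50% | 7% | 26% | 54% | 69% |
| 20 | 43% | 7% | 25% | 52% | 66% |
| 72 | 27% | 6% | 21% | 44% | 56% |

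The screen loses badly at d = 0.2. At d = 0.5 it loses 24, 18 and 6 points for 12, 20 and 72 measures. At d = 0.8 it gains 4, 9 and 17 points.

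**Step 4: false predictors without adjustment.** If no measure predicts and all are independent, the chance of at least one false finding is 1 − 0.95^M = 46%, 64% and 98% for M = 12, 20 and 72. Behind the screen, if none differs from controls, it is 1 − (1 − 0.05 × 0.05)^M = 3%, 5% and 16%. If all differ by d = 0.5, it is 1 − (1 − 0.05 × 0.338)^M = 18%, 29% and 71%. Independence is a simplification: occurrence rates sum to one and are tied to dwell times and transitions, so the unscreened figures probably overstate the risk.

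**Step 5: the two sentences side by side.** Section 1.0(c) names a broad class, and Section 4.0 names part of it. Section 4.0 contains no word such as only, no threshold and no rule for dropping a measure. An analysis of the narrower set also answers the broader question, so the sentences can be followed together.

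**The case for a change.** The best case for a change is that the sequential reading is the natural one and the protocol offers no other meaning for the label. Section 2.0 itself motivates the work by differences among patients that bear on response, which a comparison with controls does not select for. Naming one to three predictors in advance would have 84% power for one measure, or 70% for three with Bonferroni, at r = 0.6. Either exceeds the screened figures at d = 0.2 to 0.8, and the cost is one sentence in each of two sections.

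Part of this stands. The wording differs, the label is undefined, and a screen of this kind can discard a true predictor. If a screen is used, a measure that fails it is untested, not shown to be without predictive value.

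The rest does not carry a change. The 84% and 70% presuppose that the right measures can be named beforehand, which is doubtful when the stated aim is to discover biomarkers with a new method in 20 patients. Which predictors are analysed, and with what error control, is commonly settled in the SAP, which is not at hand. Limiting prediction to disease-related states is also a defensible scientific choice in an exploratory study.

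**Conclusion.** No change to the plan follows. The screen is inferred from an undefined adjective and the order of three sentences, and Section 4.0 can be read as the narrower working form of Section 1.0(c). The fall from 84% to 8–57% is correct arithmetic, but it sets a screened measure against a single unadjusted test that neither section describes. On an equal footing with 20 measures, direct power is 43%, against 25% screened at d = 0.5 and 52% at d = 0.8. Whether a screen costs or gains power therefore depends on the group difference and the number of measures, neither of which the protocol gives. These figures rest on r = 0.6, two-sided 5% tests, no dropout, and other measures that are null and independent.

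What remains is a small difference in wording. An analyst writing the SAP would resolve it by listing the predictors and saying whether the comparison with controls selects them. It is not a sample-size error.
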